The primary analysis for this study will be a mixed logistic regression model comparing BUP/NX versus MMT on viral suppression rates over time. Treatment comparisons will be performed under the Intent-to-Treat (ITT) criterion; participants will be analyzed in the arm to which they

were randomized regardless of subsequent events. In this mixed logistic model, each (binary) outcome serves as a dependent variable; treatment effect (BUP/NX versus MMT referral) and time effect (e.g., baseline, 6, and 12 months) will be considered main effects. An interaction between these two main effects, e.g., treatment*time, will be included in the model. Model-fitted, marginal risk and RD estimates will be obtained at each time by applying an inverse-logit transformation to coefficients from the logistic regression model, with standard errors estimated via the delta method. We will test the primary hypothesis of noninferiority by comparing the lower bound of a 95% confidence interval to the prespecified margin (i.e., 13%); if the lower confidence limit of the RD is greater than -13%, we will conclude that the BUP/NX is noninferior to MMT. The model will include subject-level random intercepts in order to account for repeated measurements within individuals. Attrition is unavoidable in a longitudinal study; in our study, we anticipate an attrition rate of 20%. The mixed model approach is a recommended strategy for handling missing data in clinical trials under the assumption that the data are missing at random.

We will conduct three sensitivity analyses. First, we will assume data are missing not at random and use single imputation of unsuppressed for missing VL data. Participants who are lost to follow-up will be imputed as treatment failures (i.e., not suppressed). Death from any cause and dropout will also be considered equivalent to non-suppression for the purposes of this analysis. Second, we will use multiple imputation with Markov-Chain Monte Carlo methods and “auxiliary variables” (i.e., covariates that are not part of the main analysis, but may help predict data missingness) to address missing data. We will include covariates associated with missingness at any time-points (using a relaxed p-value of 0.2) as auxiliary variables in our multiple imputation model. Finally, for our third sensitivity analysis, we will conduct a per-protocol analysis among participants who received at least one dose of study medication in the 90 days before each visit. If sensitivity analysis results change the primary outcome findings, we will report the results alongside our main analysis.

Secondary outcomes including binary ART initiation, ART adherence, and retention in HIV care will be analyzed using similar procedures. As these are superiority hypotheses, we will test them using two-tailed tests at an alpha level of .05.

Aim 2: Assess effect of clinic-based BUP/NX versus MMT referral on opioid use in HIV-infected participants with opioid dependence.

- **H2:** We hypothesize that participants randomized to BUP/NX will have a lower proportion of positive assessments for opioid use (self-report + UDS) at 12 months versus MMT referral

Overview. In Aim 2, we assess the effect of clinic-based BUP/NX on opioid use as measured by urine drug screens or any self-reported use in the last 30 days, assessed at 3, 6, 9, and 12 months following randomization.

Dependent variables. The primary dependent variable for Aim 2 will be the proportion of positive assessments for opioid use at 12 months, as measured by any self-reported opioid use or positive urine drug screen during the 12-month follow-up assessment (binary). We will consider secondary substance use outcomes including proportion of follow-up visits with a positive assessment for opioid use (proportion), and other illicit drug use (binary), and alcohol use (binary).

Power Analysis: Since our primary outcome in this aim is opioid use, the power analysis is based on this outcome. With our proposed sample size (450 as the total, 225 for each treatment arm), we have gained the power of 91% to detect 15% in difference between the two groups at

the level of alpha 0.05, provided that the proportion of UDS positive for opioid at 12 months will be 65% for MMT referral. This power analysis is conservative due to not maximizing multiple-time-point data from our longitudinal study. We anticipate the power is much higher to off-set the complexity of the mixed logistic model (adjusting for some covariates) we propose in the data analysis plan (see below).

Data Analysis Plan: The primary (binary) outcome for Aim 2 is opioid use, collected at baseline, 3, 6, 9, and 12 months. We will use an approach as in Aim 1.

Aim 3: Assess BUP/NX implementation experience to inform national scale-up of clinic-based BUP/NX.

Overview. We will conduct qualitative interviews with HIV providers, administrators, and opioid dependent participants, and their family members in participating HIV clinics annually during years 1 through 4 to document and describe formative implementation strategies, challenges, and best practices. Results inform policy-making for national scale-up of clinic-based BUP/NX in Vietnam.

Qualitative Procedures and Analysis. The implementation aim documents the experience of providers and participants at clinics to further inform adoption of BUP/NX in Vietnam and guides planning efforts and policy-making. Data also monitor the performance of the sites and qualitative interviews provide critical detail for enhanced understanding of the findings from the trial (Aim 1 and 2). Using the Taxonomy of Mixed Method Designs¹³⁴⁻¹³⁶, our design has a QUAN +Qual structure with simultaneous data collection and emphasis/weight placed on the quantitative efforts. The qualitative data provide complementary information to illuminate and expand the findings from Aims 1 and 2.

The qualitative data (recurrent and salient themes extracted from interviews) document provider, organizational, and participant experiences over time to concurrently monitor clinic-based BUP/NX and to examine these findings in parallel with outcomes data (i.e., opioid use, HIV viral suppression). The HIV clinics' characteristics and provider attitudes (inner setting), as well as detail about the use of BUP/NX (intervention characteristics), and community awareness, linkage across service settings, and policy support (outer setting) help identify the full range of complex variables associated with implementation of clinic-based BUP/NX. This approach represents an innovative strategy to integrate available quantitative study results (Aim 1 and 2) to examine the provider, participant, organizational, and policy-level changes that influence the uptake of BUP/NX in HIV clinics in Vietnam. Results are compared for convergence and the team examines concordance and discordance between study sites and across populations including providers, participants and administrators. Corresponding with the Consolidated Framework Implementation Research (CFIR) we identify individual, organizational and contextual characteristics that influence uptake of BUP/NX within the context of an RCT in HIV clinics in Vietnam.

Qualitative Analysis. Data will be catalogued in a spreadsheet within one week of a site visit to assure that all files and documents have been collected. Field notes written on site are expanded and recorded electronically within 24 hours.¹³⁷ Audio-recorded site visit interviews are professionally transcribed, reviewed and summarized. Transcriptions are password protected and stored on a secure network and uploaded into qualitative analysis software (Atlas.ti™) which organizes data and facilitates coding and thematic analysis. The qualitative analysis will be completed in Vietnamese. Selected samples of the transcripts will be translated into English and sent to trained research staff so they can review and assist in developing codes. The qualitative

team creates a coding scheme, practices coding, and revises in an iterative group process that has been successfully implemented by the study team in other mixed-methods projects.^{47, 138-141} Each transcript is coded and check-coding is completed with 20% of transcripts to ensure inter-coder reliability. Selected texts for each code will be translated into English for review by the U.S. investigator. The analysis examines the implementation process and identifies specific characteristics that facilitate use of BUP/NX in HIV clinics within the framework of the RCT (Aim 1 and 2). Iterative analyses assess convergence of CFIR participant, provider and organizational dimensions on study measures as well as the context of the policy subsystems, cross system interactions, and resource allocation. The team analyzes site visit products and identifies areas for additional data collection, assesses and ensures data quality, and produces summaries of findings shared with the Advisory Board to inform project implementation. A five phase strategy guides the analysis: describe themes, organize and structure data, connect codes and themes, corroborate and triangulate, and condense and summarize findings.¹⁴²

Privacy, Confidentiality, and Data Security

Data will be stored in a manner intended to preserve participant confidentiality. All paper files that contain study data with PHI will be kept at the study sites in locked cabinets behind locked doors that only study staff have access to. Study files with names or other identifiers are kept in a separate locked cabinet than files with study data. The only file linking the unique identifier with the participant's name is the Master Enrollment Log which is kept in separate locked cabinet than any study data.

Data will be collected using the OHSU REDCap™ electronic data collection system. REDCap™ (Research Electronic Data Capture) is a secure, web-based database application designed to support traditional case report form data capture for research studies. Data files are securely maintained behind the OHSU firewall, and not shared with other institutions. REDCap™ also facilitates data quality assurance.

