The primary objective of this proposal is to add to the palette of treatment options by comparing the effect of two opioid dependence treatment delivery models on improving the HIV care engagement and outcomes in Vietnam. We propose a multisite, open-label, randomized, flexible-dose noninferiority trial of buprenorphine/naloxone (BUP/NX) (n=225) versus methadone maintenance therapy (MMT) referral (n=225) for treatment of opioid dependence in HIV-infected participants in 6 Vietnam HIV clinic research sites. The study is conducted in partnership with colleagues at Hanoi Medical University (HMU), the Provincial AIDS Control (PAC) authorities of Hanoi, Thanh Hoa, and Bac Giang, the Vietnam National Institute of Mental Health, and Oregon Health & Science University.

Study sites are 4 HIV clinics in Hanoi, 1 in Thanh Hoa, and 1 in Bac Giang; epicenters of Vietnam's HIV and heroin epidemics, all of which are associated with MMT and HIV testing and counseling centers. A research coordinating center at HMU provides additional outreach, recruitment, non-medication-related study procedures and links participants to participating HIV clinic sites for clinical management. HIV providers will be trained to manage opioid dependence using BUP/NX.

Participants are HIV-infected participants with opioid dependence new to HIV care, recruited from HIV clinics, MMTs, and associated HIV testing centers. Participants randomized to BUP/NX will receive BUP/NX after successful completion of medication induction and stabilization. Participants randomized to BUP/NX will receive a taper after 12 months of study drug exposure, with referral for MMT. Participants randomized to MMT will receive usual care, which is case-manager-assisted referral to MMT. All participants receive clinic-based individual counseling and HIV care.

The primary outcome of HIV-1 viral load will be measured at baseline, 6, and 12 months. Secondary outcomes, including self-reported drug use, urine drug screens (UDS), and measures of HIV care engagement (adherence, retention) will be assessed quarterly through 12 months follow-up. Qualitative interviews with participants, family members of participants, and providers in years 1 through 4 will identify lessons-learned for scale-up of HIV clinic-based BUP/NX.

Figure 2. Study Schema

There are three specific aims in this protocol:

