research coordinating center at HMU provides additional outreach, recruitment, non-medication-related study procedures and links participants to participating HIV clinic sites for clinical management. HIV clinics were selected based on the prevalence of untreated active opioid dependence among new participants with a history of IDU, ability to enroll at least 120 participants over the course of the study, availability of methadone maintenance, and support of local authorities. Medical directors at participating sites estimate that < 5% of participants with active heroin use currently access MMT. All HIV clinic sites have on-site counseling, case management, phlebotomists and pharmacy services on-site, and are affiliated with Voluntary Counseling and HIV Testing (VCT) services and MMT programs in their surrounding communities that have capacity for accepting new MMT referrals.

Study Design and Procedures

450 Participants (225 BUP/NX and 225 MMT) HIV-infected participants with active opioid dependence will be enrolled in the study across participating sites. Outreach activities will seek to identify patients new to HIV care or registered for care at participating HIV clinics but not on ART, though participants are not required to be ART treatment-naïve. Participants will be enrolled in the study for approximately 12 months, with 6 research visits total.

Inclusion Criteria:

- HIV positive
- Have a current moderate to severe DSM-5 opioid use disorder
- Urine drug screen positive for opioids
- Interested in receiving treatment for opioid dependence
- Are age 18 or greater
- Are willing to practice effective method of birth control, if female

Exclusion Criteria:

- Have a known hypersensitivity to buprenorphine or naloxone
- Have an AST & ALT > 5x upper limit
- Are currently pregnant or breastfeeding
- Have a serious medical or psychiatric illness in past 30 days (e.g. opportunistic infection, psychosis) that precludes safe participation in the opinion of study physician
- Have received methadone maintenance treatment within 30 days of consent

Known vulnerable populations will be excluded from participation; this includes children, pregnant women, decisionally-impaired adults, and prisoners.

Prisoners:

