Groups and organizations that work with newly-released prisoners will also be included but will not approach individuals who are currently detained as prisoners. Detailed instructions will be provided to Vietnamese colleagues about the distinction. Researchers will meet with staff and volunteers, provide study information, and referral information only.

HIV clinic staff will screen participants at intake for study eligibility. HMU research coordinating center research staff and peer educators will approach people from community-based “hot-spots” and from people participating in existing observational research studies to offer study participation. Potential participants with a history of MMT within the past 30 days will be excluded and encouraged to follow-up with their MMT program, in order to avoid creating an incentive for participants already engaged in MMT to switch to BUP/NX. HIV clinic and research staff will approach potential participants and assess inclusion and exclusion criteria.

Consent process

Participation in the study is completely voluntary.

HIV clinic research staff will review study procedures with potential participants and collect informed consent. Study procedures will comply with International and U.S. requirements for human participant protections. Consent forms will be approved by Institutional Review Boards at OHSU and HMU, and by the Vietnam Ministry of Health Ethics Review. All consent forms will be presented to candidates in Vietnamese and will be administered by Vietnamese-speaking research staff.

There are four consents used in this study:

1. Pilot testing of study measurements
2. Pre-Screening
3. Full Study
4. Qualitative Interviews (participants, family members, providers and administrators (staff))

Compensation

All participants will be compensated for their time and effort in this study, using culturally-appropriate amounts. All compensation will be in cash and provided at the end of each visit so no pro-rating will be necessary. The following schedule will be used.

Table 1. Compensation Schedule

Visit	Amount in Vietnamese Dong	Amount in American Dollars (approximate as of October 2016)
Pre-Screening	50,000 ^d	\$2.24
Screening	200,000 ^d	\$8.97
Baseline	200,000 ^d	\$8.97
3 Month	250,000 ^d	\$11.21
6 Month	300,000 ^d	\$13.46
9 Month	350,000 ^d	\$15.7
12 Month	450,000 ^d	\$20.19
TOTAL	1,800,000 ^d	\$80.70

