Participants are randomized to clinic-based BUP/NX vs. referral for MMT. This is a non-blinded study. Randomization will be conducted by computer generated random number sequence in blocks of 10 prepared by statisticians at OHSU. Allocation assignments will be maintained in sealed, sequentially numbered envelopes by the Vietnam Research Coordinating Center (RCC) at Hanoi Medical University. HIV clinic site research assistants will call the RCC to receive allocation assignment when a participant is deemed eligible for study participation.

Pilot Data Collection and Assessments

The data collection instruments were pilot-tested with participants at four additional sites: Bac Giang PAC OPC; Bac Giang Provincial Hospital OPC; Viet Tri, Phu Tho PAC OPC; and Phu Tho Town Community Health Center OPC.

Table 2: Table of Assessments								
	Pre-Screening	Screening	Baseline	3 Month	6 Month	9 Month	12 Month	As Needed Only
Visit Window	--	60 days after Pre-Screening		+/- 14 days	+/- 14 days	+/- 14 days	-14 days/+30 days	--
Pre-Screening Consent Form	X							
Informed Consent		X						
Informed Consent Quiz		X						
Progress Note		X	X	X	X	X	X	X
Visit Checklist	X	X	X	X	X	X	X	
Locator Form	X	X	X	X	X	X	X	
Master Enrollment Log	X	X	X					
Communication Log								X
Compensation 
 • Log • Receipt 		X	X	X	X	X	X	
Data Collection Forms								
Inclusion/Exclusion Criteria (Eligibility Checklist)			X					
Pre-Screening Survey	X							
Screening Survey		X						
Baseline Survey			X					
3 Month Survey				X				
6 Month Survey					X			
9 Month Survey						X		
12 Month Survey							X	
ASI-lite Table			X	X	X	X	X	
Randomization Form			X					
Physical Exam			X					
Dosing Form 
 • BUP/NX • MMT 				X	X	X	X	
HIV Care Utilization Form				X	X	X	X	
Fatal Overdose Form								X

Table 2: Table of Assessments								
	Pre-Screening	Screening	Baseline	3 Month	6 Month	9 Month	12 Month	As Needed Only
Pregnancy and Birth Control Assessment • Includes Urine Test		X	X	X	X	X	X	
Confirmed Pregnancy Test								X
Early End of BUP/NX								X
HIV Viral Load			X		X		X	
CD4*		X*			X*		X*	
HIV genotype resistance testing (as necessary)			X				X	
HIV confirmatory testing (as necessary)		X						
HIV rapid testing	X							
Tuberculosis (PPD Skin Test)*			X*					
Hepatitis B/C*			X*					
Safety Labs* • CBC • AST/ALT •		X*						
UDS • Morphine • Methadone • Methamphetamine • Amphetamine • Buprenorphine	X	X		X	X	X	X	

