HIV clinic providers and staff will be trained in BUP/NX management of opioid dependence. Participants randomized to clinic-based BUP/NX will be evaluated by the HIV clinic study physician for symptoms and signs of withdrawal using clinically available opioid withdrawal scales and induced onto BUP/NX when in moderate withdrawal in order to avoid precipitated withdrawal (12-24 hours after last dose of short-acting opiates like heroin, and 2-4 days after last dose of long-acting opioids. BUP/NX induction begins with a 2-4 mg test dose followed by additional doses on the day of induction to relieve withdrawal symptoms, and then titrated to a maintenance dose between 8-24 mg/day over 1 to 3 days. Participants will return for daily dosing until a stable maintenance dose is reached, as determined clinically by the HIV clinic study physician. Dosing will remain flexible to a maximum dose of 24mg. After a participant is stabilized on a maintenance daily dose for at least 2 weeks, they may switch to every-other-day dosing (4 times per week), doubling the maintenance dose to a maximum of 32mg prior to “skip” days. Participants will continue to receive BUP/NX for 12 months, followed by a 14-day taper and referral to MMT. The study will use BUP/NX in a 4:1 ratio combination sublingual tablet for treatment of opioid dependence.

Referral for MMT

Referral for MMT has become the standard of care for opioid dependence in Vietnam. Participants randomized to MMT referral will meet with an HIV clinic case manager who will facilitate referral to MMT. Methadone dosing will be managed by MMT staff, who dispense methadone according to Ministry of Health guidelines for MMT.⁹⁸

[figure not shown]
Study sites and dosing sites

Participants will complete all research activities (consenting, surveys, and other data collection activities) at the six HIV clinics. Two HIV clinics (Tu Liem clinic and Long Bien clinic) will serve only as clinical management and medication dispensing sites, with non-medication study procedures being performed by Vietnam Research Coordinating Center (HMU) research staff.

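### One printed block size of 10 in a non-blinded trial, with the envelopes held by a coordinating centre that also recruits, leaves up to one assignment in six predictable to centre staff who can follow the whole sequence

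*Combined protocol and SAP*

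**What the plan says.** The Randomization section sets out the mechanism in four statements.

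- On masking: "This is a non-blinded study".
- On the list: "Randomization will be conducted by computer generated random number sequence in blocks of 10 prepared by statisticians at OHSU".
- On custody: "Allocation assignments will be maintained in sealed, sequentially numbered envelopes by the Vietnam Research Coordinating Center (RCC) at Hanoi Medical University".
- On release: "HIV clinic site research assistants will call the RCC to receive allocation assignment when a participant is deemed eligible for study participation".

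Three other sections describe what else the RCC does.

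- Objectives: "A research coordinating center at HMU provides additional outreach, recruitment, non-medication-related study procedures".
- Recruitment Methods: "HMU research coordinating center research staff and peer educators will approach people from community-based" meeting places and from existing observational studies.
- Study sites and dosing sites: two clinics only manage and dispense treatment, with "non-medication study procedures being performed by Vietnam Research Coordinating Center (HMU) research staff". The same section counts consenting and surveys among the research activities.

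The protocol does not mention stratification by clinic, varied block sizes, withholding of the block size from recruiting staff, or a division of duties within the RCC between those who open envelopes and those who recruit.

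**The concern.** Telephone release from a central holder conceals the next assignment well when the holder takes no part in deciding who enters and when. Here the unit that answers the telephone also finds candidates and, for two clinics, carries out research procedures. Because treatment is open, past assignments can become known. With one constant block size, anyone who follows the list can count down to the end of each block.

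The stake is selection bias. A member of staff who knew or suspected the next assignment could bring a candidate forward, delay one, or lean on a discretionary eligibility judgement. Screening may follow pre-screening by up to 60 days, and one exclusion rests on the study physician's opinion. Participants need not be ART-naive, so their outlook for 12-month viral suppression can differ widely at entry. The primary model contains treatment, time and their interaction. Baseline covariates are listed only as potential ones.

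**Working it through.** **Inputs.** Block size is 10 (Randomization). Planned allocation is 225 and 225, total 450 (Study Design and Procedures: "450 Participants (225 BUP/NX and 225 MMT) HIV-infected participants with active opioid dependence will be enrolled"). A 5:5 split within each block is inferred from that equal allocation. There are six clinics (Objectives). The noninferiority margin is 13 percentage points (Noninferiority Margin). The protocol gives no predictability figure of its own to reproduce. Its design is consistent with 450/10 = 45 complete blocks.

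**1. Certain assignments, full view.** The observer knows the block size, the block boundaries and every earlier assignment. With m places per arm in a block, the expected number of assignments fixed by the earlier ones is 2m/(m + 1). For m = 5 this is 10/6 = 1.667 per block of 10, or 16.7%. Over 45 blocks: 45 × 1.667 = 75 of 450. An exact recursion over the 5:5 block gives the same 5/3.

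**2. Best guess, full view.** Always guessing the arm with more places left is right 65.3% of the time, against 50% by chance.

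**3. Partial view of one central list.** Suppose a recruiter sees only a random share of the list but knows the position within each block. An assignment is then certain only when all five places of one arm have been seen. Simulated results (the shares are assumptions):

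| Share of list seen | Assignments known with certainty |
|---|---|
| 1/6 | about 0.001% |
| 1/3 | 0.07% |
| 1/2 | 0.5% |
| 2/3 | 2.2% |
| all | 16.7% |

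**4. If the list is stratified by clinic.** Assume six clinics of 75 each. Each has seven complete blocks and five places of an eighth, and those first five places add no certain assignments. The total is 6 × 7 × 1.667 = 70, and 70/450 = 15.6%. Here clinic staff would see the whole of their own sequence.

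**5. Effect of varying the block size.** Block sizes were drawn at random from 6, 8, 10 and 12, for an observer who sees the full sequence and knows the set of sizes but not the boundaries. Simulation gives about 0.8% certain assignments. Guessing the arm that is behind is still right 65.7% of the time, because that guess needs no knowledge of the block size.

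**6. Possible size of bias (illustration, upper bound).** Suppose all 75 certain places were steered, about 37.5 per arm. Suppose also that the people steered to one arm differed from those steered to the other by 10 to 30 points in their probability of suppression (assumed). The risk difference would shift by 37.5/225 = 1/6 of that gap. That is 1.7 points (10/6) to 5.0 points (30/6), in either direction, against a margin of 13.

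**The case against.** The strongest reply is that the plan already has real safeguards. The list is made by statisticians elsewhere, the envelopes are sealed and numbered, and sites telephone only once eligibility has been decided. As written there is one central list with no stratification, so a clinic assistant sees too little of it to predict anything. The protocol does not say that envelope custodians and outreach staff are the same people, that outreach staff see a running list, or that recruiters are told the block size. Candidates pass through pre-screening, screening and baseline while several clinics draw on the same list, so aiming one person at one place would be hard. The viral load is measured in a central laboratory.

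Much of this stands. A reader might infer that the design makes one assignment in six predictable to recruiters in general. The text does not support that: 16.7% is a ceiling for someone with the full sequence, the block size and the boundaries. A reader might also infer that steering took place, and nothing in the protocol suggests it. Nor is it right that no analysis could help. Adjustment can address measured factors such as ART status, but the primary analysis does not commit to it, and unmeasured selection would remain.

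What the reply does not settle is the RCC's double role. Sealed envelopes and telephone release protect against a caller who does not know the sequence. They protect less when the unit opening the envelopes also recruits, and for two clinics the RCC may be on both sides of the call. The Consent process section assigns consent to clinic research staff, so the split of duties at those two clinics is not clear. Central laboratory measurement protects outcome assessment, not selection at entry.

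**Conclusion.** The concern holds in a limited form. A single printed block size, open treatment and RCC custody without stated separation from recruitment leave an avoidable weakness in allocation concealment. Its size is at most 16.7% of assignments (about 75 of 450) for RCC staff with the full view. It is near zero for clinic staff under one central list, and about 15.6% within clinics if the list is stratified with equal clinic sizes. These figures assume 5:5 blocks. Whether anyone has the full view is not stated.

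The bias illustration of 1.7 to 5.0 points is an upper bound that rests on assumed prognosis gaps and complete steering. It shows that the matter is not negligible beside a 13-point margin, but it does not estimate bias in this trial. This is a worthwhile, cheap improvement and not a defect that invalidates the comparison.

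**What to change.** For assignments not yet made:

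1. Replace the fixed block with randomly ordered block sizes, for example 6, 8, 10 and 12. Keep them out of the protocol and known only to the statisticians who prepare the list.
2. Have the envelopes held and opened by existing RCC staff who have no recruiting, consenting or eligibility role, and state this in the Randomization section.
3. Release each assignment only after the eligibility checklist and baseline survey are saved in REDCap with a time stamp, including for the two clinics served by RCC staff.
4. State whether the list is stratified by clinic.

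Step 1 alone is not enough, since it removes nearly all certain assignments but does not improve the best guess. Steps 2 and 3 carry the rest.

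The cost is a regenerated list for the remaining places, a few protocol sentences and a small change in RCC duties. REDCap and real-time entry are already in use. The drawback is a slightly larger possible imbalance at the end of the trial.

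The protocol does not give enrolment status. If enrolment is complete, report who could see the sequence and compare baseline ART status and viral load by arm among late-block assignments. With about 75 certain places in all, that comparison could show gross steering but could not exclude a modest amount.
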